## Study Design and Methods

### Overview of the Research Paradigm

### 1-year Follow-up

Patients will be contacted monthly for 1 year following completion of exercise training to determine continued exercise habits, the amount of re-hospitalizations, acceptance to a lung transplant waiting list, and mortality rate.

To qualify for participation, subjects will undergo physical evaluation by a credentialed member of the Rehabilitation Medicine Department's medical staff to determine if they meet the inclusion and exclusion criteria. At this time, subjects must answer "no" to the question "do you currently participate, or within the past six months have you regularly participated, in a structured exercise program greater than 30 minutes a day for 3 or more days a week." Subjects answering "no" to this question, and meeting other inclusion/exclusion criteria will then undergo an EKG and Doppler echocardiography to rule out pulmonary hypertension and right and left ventricular dysfunction. In addition, they will have pulmonary function testing with DLCO to rule out COPD and to assess lung diffusion capacity. Subjects will also undergo a blood draw for two tests: Nt ProBNP and Complete Blood Cell Count with Differential. Qualified participants will then receive the baseline research test battery, which includes 6MWT, tCPET with cardiac output and muscle oxygenation measurements, and questionnaires to measure patient-reported fatigue severity, physical activity, and other HRQoL domains.

After completion of the baseline research test battery, subjects will be randomized to one of two groups. The randomization design will be a 2x2 block randomization in which subjects will be randomized in pairs. The first subject will be assigned to either a control group that receives 10-weeks of patient education lectures (1 day per week, 1 hour each lecture) with no AET or an intervention group participating in AET, 3 days per week for 10 weeks, in addition to the educational lectures (AET+). The second subject of the pair will be assigned to the opposite group.

After completion of the AET+ or control regimens, subjects will undergo the follow up research test battery. The follow up battery consists of echocardiogram, pulmonary function test, arterial occlusion muscle oxygenation test, 6MWT, tCPET, and questionnaires identical to those included in the battery at baseline. Subjects in the control group will subsequently participate in a 10-week AET regimen identical to AET+ except without the educational lectures, since participation in the lectures was completed as the control condition. A second identical, follow up test battery will be completed by this group after the crossover AET regimen is completed. After completion of their AET+, subjects will be contacted monthly with regard to continued exercise habits, the frequency, length, and severity of hospitalizations, or acceptance to a lung transplant waiting list. Mortality will also be assessed at this time.

**Specific Aim 1:** "Determination of the Influence of AET+ on PWC in Patients with ILD".

The main outcome variable for this project is 6MWT distance, which is the most frequently used measure of physical performance for evaluating patients with ILD and other advanced lung diseases. A minimal clinically important difference (MCID) for 6MWT distance has been determined to be approximately 30 meters in ILD. Additional measures of PWC used in this study are peak WR on the tCPET, and performance and perceived fatigability as measured by a modification of the method used by Schnelle and coworkers in an older cohort. We will measure all 4 of these variables at baseline and after the AET+ and control regimens, as well as after the crossover regimen. We hypothesize that:

- 1.1. An increase in 6MWT distance of at least 30 meters longer than control will be observed after AET+.
- 1.2. A significant increase in peak WR will be observed after AET+ compared to control.
- 1.3. A significant decrease in performance fatigability will be observed after AET+ compared to control.
- 1.4. A significant decrease in perceived fatigability will be observed after AET+ compared to control.

- 1.5 In the Sub-study on Crossover we hypothesize that AET will result in improvements over baseline in all of the variables of interest including 6MWT, peak WR, and performance and perceived fatigability that are similar to AET+.

**Specific Aim 2:** “Characterization of the Cardiorespiratory Adaptation to AET in Patients with ILD.” Measures of cardiorespiratory capacity are often influenced by subjective factors such as motivation and confidence. Our measures of cardiorespiratory capacity in this project are AT-time, and muscle oxygenation capacity. Neither of these physiological measures is influenced by subjective factors. We will measure AT-time during tCPET and muscle oxygenation by arterial occlusion testing at baseline and after the AET+ and control regimens. We will also measure Qt, peak VO2, PETO2 and PETCO2 during tCPETs at baseline and after the AET+ and control regimens. We will measure all of the variables again after the group initially completing the control regimen completes the crossover AET regime. We hypothesize:

- 2.1. After the AET+ regimen, AT-time will be significantly prolonged over controls.
- 2.2 After AET+, a significant increase in muscle oxygenation capacity will be observed over controls.
- 2.3 Qt, peak VO2, PETCO2 and PETO2 will remain unchanged following both AET+ and control regimens.
- 2.4 In the Sub-study on Crossover we hypothesize that AET will result in improvements over baseline in all of the variables of interest including AT-time and muscle oxygenation that are similar to AET+. We also hypothesize that Qt, peak VO2, PETO2 a PETCO2 will remain unchanged over baseline after AET.

**Specific Aim 3:** “Determination of the Influence of AET on Patient-reported Measures of Fatigue, Physical Activity, and Other HRQoL Domains in Patients with ILD.” We will use the Fatigue Severity Scale (FSS) to assess fatigue severity, Human Activity Profile (HAP) to assess participation in physical activities, SF-36v2 to assess general HRQoL, Profile of Mood States (POMS) to assess changes in mood, and Kings Brief Interstitial Lung Disease Health Status Questionnaire (K-BILD) to assess HRQoL specific to ILD. We will also use the St. Georges Respiratory questionnaire to assess HRQoL specific to IPF. Subjects will answer the questionnaires before and after the AET+ and control regimens. Subjects in the group receiving the control regimen will again answer the questionnaires after completing the crossover AET regimen. We hypothesize

- 3.1. After AET+, fatigue severity will be diminished over control.
- 3.2. After AET+, participation in physical activity will be increased over control.
- 3.3. After AET+, overall mood will be increased over control.
- 3.4 After AET, general HRQoL and HRQoL specific to ILD and IPF will all be improved over control.
- 3.5 In the Sub-study on Crossover we hypothesize that AET will result in improvements over baseline in all of the variables of interest including fatigue severity, physical activity, mood state, and HRQoL that are similar to AET+.

**Specific Aim 4:** “One-year Follow Up on Hospitalization, Lung transplant, and Mortality.” In this follow up sub-study, patients will be contacted monthly for one year after completing AET+ regarding frequency and type of exercise subjects have continued; number and nature of hospitalizations; days spent in the hospital; and the severity of their condition causing hospitalization. Subjects’ acceptance onto transplants lists and patient mortality will also be determined. We will examine potential associations among these variables and our variables of interest to determine plausibility of relationships between study outcomes and clinical endpoints.

Two corollary hypotheses will be examined: i) poor clinical outcomes are associated with the severity of cardiorespiratory impairment, and ii) AET-induced improvements in these outcomes are associated with improvements in cardiorespiratory capacity

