## Research Objectives:

The objectives of the work proposed are, in patients who have ILD, to:

1. Determine the safety and tolerability of exercise training in patients with ILD to determine appropriate pulmonary rehabilitation exercise guidelines.
2. Examine responses and adaptations to exercise at quantifiable target intensities that correspond to energy expenditure requirements.
3. Understand changes in the symptom limited exercise test results, using training-specific testing modalities.
4. Examine the effects of exercise training on physical activity functioning.
5. Determine the relationships between patient's ability to achieve and maintain an aerobic steady state and to sustain physical activity.
6. Determine the effect of aerobic exercise training on psychosocial and behavioral functioning and other HRQOL components.
7. Based on the progression in training volume, delineate the time course of improvement in work capacity across an aerobic exercise training program.
8. Explore the relationships among measures of aerobic metabolic function and potential mechanistic factors that may limit oxidative metabolism.
9. Examine the relationships among indices of aerobic metabolic function and the mechanisms by which aerobic exercise training improves oxidative metabolism.

[figure not shown]
To accomplish these objectives, we will perform a RCT comparing a 10-week, interventional regimen of AET plus patient education (AET+) to a control condition of patient education only (CON) that does not include AET. A secondary study will also be conducted using a single "crossover" design in which the patients randomized to the control arm of the main study will receive AET after they are finished the 10-week education only regimen.

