## **Our Specific Aims are:**

1. “Determination of the Influence of AET+ on PWC in Patients with ILD”.  
Specific Hypothesis: AET+ will improve measures of PWC, including our main outcome variable 6MWT distance, and peak WR, as well as performance and perceived fatigability over controls.  
*“Sub-study On Crossover:”* After completing the education-only regimen and subsequently completing the AET regimen, improvements similar to AET+ will be observed in 6MWT distance, peak WR, and fatigability.
2. “Characterization of the Cardiorespiratory Adaptation to AET in Patients with ILD.”  
Specific Hypothesis: After AET+, significant increases in AT-time and muscle oxygenation will be observed over control.  
*“Sub-study On Crossover:”* After completing the education-only regimen and subsequently completing the AET regimen, improvements similar to AET+ will be observed in AT-time and muscle oxygenation capacity.
3. Determination of the Influence of AET on Patient-reported Measures of Fatigue, Physical Activity, and Other HRQoL Domains in Patients with ILD.”  
Specific Hypothesis: After AET+, patients will report decreased fatigue severity measured by the Fatigue Severity Scale, increased physical activity measured by the Human Activity Profile, and improvement in other HRQoL domains measured by the St. Georges Respiratory Questionnaire and SF-36v2 over control.  
*“Sub-study On Crossover:”* After completing the education-only regimen and subsequently completing the AET regimen, improvements similar to AET+ will be observed in fatigue severity, physical activity and other HRQoL domains.
4. “One-year Follow Up on Hospitalization, Lung transplant, and Mortality.”  
This is a descriptive analysis to examine health outcomes of frequency, length and severity of hospitalizations, acceptance onto a lung transplant waiting list, and mortality occurring over the year after completion of the main study.

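### Aim 4's one-year window opens at week 10 in one section and, for CON, at about week 20 in three others, and subjects who do not complete AET never enter it

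*Combined protocol and SAP*

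**What the plan says.** All references are to the combined protocol and SAP. Four places set the start of the one-year follow-up.

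- Our Specific Aims, Aim 4: health outcomes including "mortality occurring over the year after completion of the main study".
- Study Design and Methods, 1-year Follow-up: "Patients will be contacted monthly for 1 year following completion of exercise training".
- The design narrative in the same section: "After completion of their AET+, subjects will be contacted monthly with regard to continued exercise habits".
- The detailed Specific Aim 4 paragraph: "patients will be contacted monthly for one year after completing AET+ regarding frequency" and type of exercise, hospitalizations, transplant listing and death.

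The timetable for CON comes from two places. Research Objectives treats the crossover as a secondary study, in which "patients randomized to the control arm of the main study will receive AET after they are finished the 10-week education only regimen". The design narrative adds: "Subjects in the control group will subsequently participate in a 10-week AET regimen identical to AET+ except without the educational lectures". It then states: "A second identical, follow up test battery will be completed by this group after the crossover AET regimen is completed".

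Three other provisions matter. Exclusion Criteria lists acceptance for transplant as an exclusion. Monitoring Subjects and Criteria for Withdrawal takes off study any enrolled subject who later meets an exclusion criterion. The Analysis section plans correlations between post-study physiological values and health outcomes for Aim 4, with no comparison of arms.

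**The concern.** In the AET+ arm every version of the start date falls at about week 10, so the wording does no harm there. In CON the versions separate by the length of the crossover regimen. Staff reading the aim would begin calls at week 10; staff reading the methods would begin at about week 20. The plan does not say which governs, and it does not say how subjects who fail to complete training are followed.

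Two things are at stake. The first is completeness: a hospitalization, listing or death in CON between weeks 10 and 20 lies inside the window that the aim defines but before the contacts that the methods specify. The second is selection on completion. The detailed Aim 4 text asks whether poor clinical outcomes go with more severe cardiorespiratory impairment. If entry requires finishing AET, subjects who die, are listed or stop before that point are missing, and they may belong to the severe end of the range that the correlation needs.

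**Working it through.** The plan states no figure on this point, so there is nothing to reproduce. The check is timeline arithmetic.

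**Inputs.** Each regimen lasts 10 weeks (Study Design and Methods). The recruitment script describes the CON group as lasting 20 weeks. Follow-up lasts one year, taken as 52 weeks. The target is 30 completers per arm (Sample Size). Time runs in weeks from the start of the assigned regimen.

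**Step 1: what AET+ means for CON.** Research Objectives defines AET+ as training plus education, and the crossover omits the lectures. The Analysis section, however, uses the label AET+ for the regimen that CON receives in the crossover. On that usage the two statements keyed to AET+ agree with the one keyed to exercise training, and four statements reduce to two start dates.

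**Step 2: the windows.**

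| Start of the year | AET+ | CON |
|---|---|---|
| End of main study (Aim 4 statement) | 10 to 10 + 52 = 62 | 10 to 62 |
| End of exercise training or AET+ (the other three) | 10 to 62 | 10 + 10 = 20, to 20 + 52 = 72 |

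**Step 3: size of the gap.**
- Lag in CON: 20 − 10 = 10 weeks. In AET+: 10 − 10 = 0.
- Share of the aim's window with no specified Aim 4 contact in CON: 10/52 = 19%.
- Over 30 CON completers: 30 × 10 = 300 patient-weeks, or 300/52 = 5.8 patient-years.
- Over both arms: 300/(60 × 52) = 9.6% of the planned follow-up time.

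The 300 patient-weeks belong to subjects who did complete, so the Aim 4 events at risk of being missed in that time are chiefly hospitalizations. Deaths and listings in weeks 10 to 20 fall on subjects who do not complete and so are not among those 30.

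**Step 4: conditions for entry.** Under the three contact statements an AET+ subject must complete 10 weeks on protocol and a CON subject 20. Completion is required in both arms; the length differs.

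**Step 5: transplant listing.** A CON subject listed in weeks 10 to 20 meets an exclusion criterion, goes off study before finishing AET, and so never starts the monthly contacts. An AET+ subject listed in the same weeks is already in follow-up, where listing is one of the outcomes asked about.

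**Step 6: the correlations.** CON has test batteries at about weeks 10 and 20 after baseline. The Analysis section does not say which supplies the post-study value.

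**The case against.** The strongest defence is that three of the four statements agree. Every subject's year starts when that subject finishes AET, and only the Aim 4 statement is out of line. That clock also suits part of the aim: the second corollary hypothesis concerns improvements induced by AET, and the calls ask about continued exercise. For CON neither exists until the crossover is done. Starting CON at week 10 places 10 weeks of supervised training inside its year and none inside the AET+ year. This stands, and it is why the post-AET year should be kept. It does not settle which window the event counts use, and it gives no rule for non-completers.

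Some stronger readings are tempting, but the documents do not support them.

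- A reader might infer that CON is unobserved in weeks 10 to 20. CON attends supervised sessions three times a week, is asked about symptoms on each study day, has adverse events monitored and is retested. What is missing is Aim 4 contact and a rule for counting events.
- A reader might infer from the definition of AET+ that CON gets no follow-up at all. The usage in the Analysis section defeats this.
- A reader might infer that CON would look healthier than it was. Entry depends on completion in both arms, no arm comparison is planned, and CON has also had AET by then. The direction of any bias is not shown.
- A reader might take 60 completers out of 80 (75%) as a guide to crossover dropout. The 80 are counted from consent and screening, so the ratio includes screen failures. Recruitment also stays open until 30 per arm complete, so dropouts are additional to those 30. The documents give no crossover attrition rate.

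**Conclusion.** The inconsistency is real and worth correcting, with limited reach. The Aim 4 statement gives CON a window of weeks 10 to 62; the other three give about weeks 20 to 72. As written, 10 of the 52 weeks in the aim's window carry no specified Aim 4 contact in CON, events in those weeks have no rule that counts them, and non-completers in either arm never enter. A CON subject listed for transplant in weeks 10 to 20 is lost to an aim that names listing as an outcome.

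This rests on two readings: that the main study means the 10-week randomized comparison, as Research Objectives implies, and that AET+ covers the crossover regimen, as the Analysis section implies. If the main study were meant to include the crossover, the dates would agree, but selection on completion and the listing problem would remain.

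The consequence is confined to the descriptive event counts and the Aim 4 correlations. The number of events affected cannot be estimated from the documents.

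**What to change.** Reconcile the Aim 4 statement, the 1-year Follow-up paragraph, the design narrative and the detailed Specific Aim 4 text, and label each window explicitly.

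1. For the event counts, record hospitalization, transplant listing and death for every randomized subject from one common date (the week-10 test date or randomization), whether or not AET is completed.
2. For CON in weeks 10 to 20, collect these events at the crossover sessions already scheduled and mark the period as in training.
3. Keep the post-AET year as a second, separately labelled window for the exercise-habit questions and the AET-improvement hypothesis.
4. Reconcile the off-study rule with Aim 4, so that a subject taken off study, including for transplant listing, still has outcomes recorded unless the subject declines contact. This concerns data collection only.
5. State in the Analysis section which CON battery, week 10 or week 20, is the post-study value.

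The cost is protocol wording and monthly calls to the few subjects who stop early. No new visits are needed.

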use or the patient began using supplemental oxygen during the exercise training, all post-training exercise tests will be performed with the same oxygen device/flow used in the baseline testing to maintain consistency between tests.

Blood glucose of diabetic patients will be monitored before and after training, or as clinically appropriate. If training at NIH CC, glucose monitoring will be performed by qualified staff using NIH glucometer or patient's own glucometer (if first validated for accuracy through the NIH Department of Laboratory Medicine). If training at Inova Fairfax, blood glucose monitoring will be performed per Inova policy.

The locations for this intervention will be Inova Fairfax Hospital and the NIH CC. At NIH, the intervention will take place in the Clinical Center Fitness Center located in room 7-3551 on the 7th floor of the Clinical Center and will be led by trained NIH AI staff. This room has three treadmills that are currently used for aerobic training of CC patients.

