## **Participant Inclusion and Exclusion Criteria**

**See Appendix 2 for the Inclusion/Exclusion Checklist that will be used.**

### **Inclusion Criteria**

**ILD Groups:** Subjects in this study will include individuals with ILD who are referred for Pulmonary Rehabilitation. The following list provides more specific inclusion criteria:

- Between age 21-80 years.
- NYHA functional class II or III, will accept NYHA functional class I and IV based on 6 minute walk test results ( $\leq 400$  meters for Class I and  $\geq 50$  meters for Class IV)
- No episodes of syncope or significant chest pain for at least one month.
- No prior Pulmonary Rehabilitation received within the last 6 months and not currently in a maintenance program.
- Physically inactive, no participation in a structured exercise program as defined as more than 30 minutes of exercise 3 or more days a week within the last 6 months.
- Patients may qualify if they have any one of the following conditions:  
Interstitial lung disease, including idiopathic pulmonary fibrosis (IPF), non-specific pulmonary fibrosis (NSIP), sarcoidosis or other form of chronic lung fibrosis based on clinical context via clinic note from primary pulmonologist
- Low to intermediate probability of pulmonary hypertension as determined by tricuspid regurgitation velocity (TRV) at rest on echocardiogram and the presence of additional echocardiographic variables such as right ventricular size and pressure, pattern of blood flow velocity out of the right ventricle, the diameter of the pulmonary artery and an estimate of right atrial pressure. If the patient has had a recent right heart catheterization showing a mean PAP  $< 25$  mmHg, ruling out pulmonary hypertension..

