### **Other Exclusions:**

- The age range of the subjects will be limited to those between 21 and 80 years because the normal adaptive processes to aerobic exercise are generally less well understood in the childhood, adolescent, and aged subset of the population, and reference ranges for many of the exercise response variables are less well accepted than in the general adult subset. The age range of 21 to 80 encompasses the range generally referred to in the Inova Fairfax pulmonary rehabilitation program, which is one of the few pulmonary rehabilitation programs in existence serving patients who have advanced lung disease
- Subjects will not typically include individuals in Class I because patients are usually in Class II or III at the time of diagnosis.

- Subjects in NYHA Class IV will typically be excluded as the instability of their symptoms is a contraindication for exercise testing or training by nearly all published guidelines.
- Subjects in Class I may be included if they walk less than 400 meters during a six-minute walk test.
- Subjects in Class IV may be included if they are able to walk at least 50 meters during a six-minute walk test.
- Subjects with severe Raynaud’s phenomenon will be excluded from participation in the arterial occlusion muscle oxygenation capacity test.

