**New York Heart Association Functional Classification**

Class	Patient Symptoms
Class I (Mild)	No limitation of physical activity. Ordinary physical activity does not cause undue fatigue, palpitation, or dyspnea (shortness of breath).
Class II (Mild)	Slight limitation of physical activity. Comfortable at rest, but ordinary physical activity results in fatigue, palpitation, or dyspnea.
Class III (Moderate)	Marked limitation of physical activity. Comfortable at rest, but less than ordinary activity causes fatigue, palpitation, or dyspnea.
Class IV (Severe)	Unable to carry out any physical activity without discomfort. Symptoms of cardiac insufficiency at rest. If any physical activity is undertaken, discomfort is increased.

**Monitoring Subjects and Criteria for Withdrawal from the Study:** Subjects will be followed carefully during the study. At the start of each study day, subjects will be asked whether they are experiencing any unusual symptoms, and vital signs will be measured (pulse rate, oxygen saturation, resting blood pressure). All subjects will undergo EKG and echocardiography before and during the symptom limited exercise test. We will monitor heart function in the rehabilitation medicine exercise lab during exercise, and stop the exercise if there are any signs of heart problems.

Subjects enrolled who subsequently meet the exclusion criteria above at any time during the protocol will be excluded (off-study exclusion criteria).

[name], as the Principal Investigator, will make the decision to include or exclude potential participants based on their meeting inclusion, exclusion or off-study exclusion criteria.

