## **Pre-screening at Inova Fairfax Hospital as an Activity Preparatory to Research**

Inova will refer the patients to NIH after patient signs release of information authorization. The NIH Associate Investigator and Study Coordinator will have physical access to the medical records of the Inova Advanced Lung Disease (ILD) Clinic and Pulmonary Rehabilitation Department referral patients for purposes of pre-screening Inova patients and patient referrals for this study. NIH investigators represent that (1) the use or disclosure of these records is solely to review PHI as necessary to aid study recruitment, (2) the PHI will not be removed from the covered entity (Inova Fairfax Hospital) in the course of review, and (3) the PHI for which use or access is requested is necessary for the research.

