If, based on this interaction, we think the subject might meet the inclusion criteria for the study, we will request medical records (recent history, medication list, pulmonary function test, resting EKG, six minute walk and echo) to further evaluate their eligibility for the study. Potential participants can either send us their medical records or they can fill out a medical release document and we will request this information from their physician prior to their visit to NIH. Their medical records will be reviewed and, if it appears that the patient meets the inclusion criteria, we will set

up an appointment for the patient to come to the NIH Clinical Center for consent and testing. If, after obtaining a patient's medical records it is clear that the patient does not meet inclusion criteria, the information may be used to refine our inclusion and exclusion criteria; however, these medical records will not be used for any research purposes.

To prepare for the visit, we will enter their personal information into the NIH Admissions Travel and Vouchers system and an NIH patient number will be assigned to them. Upon arriving at the NIH, the patient will proceed through admissions and then consented to the study, followed by a history and physical, blood draw, ECG, transthoracic echocardiogram, pulmonary function testing, arterial occlusion muscle oxygenation capacity test, cardiopulmonary exercise test, questionnaires, and six minute walk test.

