### **Data and Safety Monitoring Plan:**

As the PI, [name] will closely monitor patient safety throughout the duration of the study. However, this protocol has several characteristics that suggest a more extensive data monitoring procedure. First, the risk of performing several exercise tests on patients with interstitial lung disease is unknown. We suspect that the risk is a minor increase over minimal risk, but we are not sure. Second, the protocol involves randomization and blinding. Patients will be randomized, to either education or exercise + education. In addition, while the subjects will not be blinded to their treatment allocation, the study personnel will be blinded to the extent that is possible with exercise intervention trials. Study personnel will be blinded through initial baseline screening/testing and randomization, however following randomization due to the nature of exercise training and the time points involved in this study the blinding process will no longer be possible. Finally, this study involves one extramural site: Inova Fairfax Hospital..

Given these additional factors, we feel that our plan may need more than just PI monitoring, but fails to meet the criteria for the involvement of a full DSMB. Therefore, we have enlisted the assistance of [name], MPH, Chairman of the Department of Physical Medicine and Rehabilitation at the Montefiore Medical Center/Albert Einstein College of Medicine, New York, as the independent medical monitor (IMM) for this study. He will be apprised of all significant adverse events. In addition, this monitor will also have access to the study data. RMD's Epidemiology and Biostatistics Department will examine the results on an interim basis. If, at any point, they feel that the study should be stopped because of concern for safety of study subjects, they will inform the PI, the IRB, and the clinical and scientific directors of CC and NHLBI.

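### The printed pair rule can make up to half of allocations predictable, so concealment before the second subject's screening and baseline tests is not assured.

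*Combined protocol and SAP*

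**What the plan says.** Study Design and Methods (text under 1-year Follow-up) places randomization after the baseline battery. It describes a 2x2 block design in which subjects are randomized in pairs: the first goes to either arm, and "The second subject of the pair will be assigned to the opposite group". The Randomization paragraph under Research Tests gives balance and avoiding early filling of one group as the purpose of blocking. It names an independent randomizer with no other part in the study. It does not mention varied or undisclosed block sizes.

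On blinding, the Data and Safety Monitoring Plan says: "Study personnel will be blinded through initial baseline screening/testing and randomization, however following randomization due to the nature of exercise training". The remainder of that sentence concedes that staff can then no longer be kept blind.

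Several steps before assignment involve people who may know earlier allocations, or involve judgement:

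- Training at NIH "will be led by trained NIH AI staff" (AI is Associate Investigator in the List of Abbreviations).
- The same role pre-screens: "The NIH Associate Investigator and Study Coordinator will have physical access to the medical records of the Inova Advanced Lung Disease (ILD) Clinic".
- After the telephone interview, staff who think a subject might qualify request records ("resting EKG, six minute walk and echo) to further evaluate their eligibility for the study").
- The Inclusion Criteria state that the study "will accept NYHA functional class I and IV based on 6 minute walk test results", and Other Exclusions puts this permissively: "Subjects in Class IV may be included if they are able to walk at least 50 meters during a six-minute walk test".
- The principal investigator "will make the decision to include or exclude potential participants based on their meeting inclusion, exclusion or off-study exclusion criteria".

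**The concern.** An independent randomizer and assignment after baseline conceal a list only if the list cannot be worked out. Here every second entry follows from the one before it by a rule printed in the protocol, and the earlier arm is open. For a second-of-pair subject, the statement that personnel are blind through screening, baseline and randomization therefore depends on nobody connecting two known facts.

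What is at stake is selection. A person who knows the next arm can, without intending to, invite, defer or exclude a candidate according to that arm. The two groups are then no longer comparable by design. The protocol itself (Informational Gaps) says that six-minute walk results may be influenced by motivation and familiarity, and gives this as a reason for a randomized trial. Sound concealment is part of what that trial is meant to supply.

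**Working it through.** The plan gives no figure for predictability, so there is none to reproduce. Its power figures are not affected by this point.

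**Inputs.** Block size 2 with the second member in the opposite arm (Study Design and Methods); 60 subjects, 30 per arm (Sample Size); arms open after randomization (Data and Safety Monitoring Plan). The target of 60 counts completers, and the number randomized is not given.

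**Ceiling under the pair rule.** Suppose pairs fill in sequence and the first arm is known in time.

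- Certain in advance: one of every two, so 60 / 2 = 30 of 60 (50%).
- Best guess correct: (0.5 + 1) / 2 = 75%, or 45 of 60, against 30 expected by chance.
- If 80 were randomized, the ceiling would be 80 / 2 = 40.

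**If only some pairs are exposed.** Let q be the share of pairs in which the first arm is known before the second subject is assessed. The documents do not give q, so the full range is shown. The number certain is 30q and the guess rate is 0.5 + 0.25q.

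| q | certain, of 60 | best-guess rate |
|---|---|---|
| 0 | 0 | 50% |
| 0.25 | 7.5 | 56.25% |
| 0.5 | 15 | 62.5% |
| 0.75 | 22.5 | 68.75% |
| 1 | 30 | 75% |

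The row q = 0 is the case in which both members of every pair finish baseline before either is assigned. The phrase about randomizing in pairs permits that reading, but the protocol does not require it.

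**Alternatives, full history known.**

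- Fixed blocks of known size, by enumeration: size 4 gives 33.3% certain (20 of 60) and 70.8% guessed; size 6 gives 25% certain (15 of 60) and 68.3% guessed. Larger blocks alone are therefore not enough if their size is known.
- Blocks of 4 and 6 chosen at random, by simulation (N = 60, 4,000 runs; the observer knows that both sizes are in use and knows the history, but not the current block size): about 5.7% certain (0.057 × 60 = about 3.4 subjects) and about 69% guessed (0.69 × 60 = about 41). The largest arm imbalance is 3, and the average at subject 60 is about 0.5.

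Certainty nearly disappears. Correct guesses above chance fall from 45 − 30 = 15 to about 41.4 − 30 = 11.4, a reduction of about a quarter.

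**The case against.** The protections are real. The randomizer is independent, assignment follows baseline, most entry criteria are numeric or diagnostic, and a credentialed physician or staff member examines each subject. The principal investigator's decision is tied to the listed criteria. Many candidates are first identified by Inova clinic staff or by the rehabilitation registrar, who may not follow the NIH enrolment order, and training at Inova could make earlier arms less visible. No text says that the same individuals both train and pre-screen. All of this stands. It lowers the likelihood that the rule is exploited, but none of it hides a published rule.

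A reader might go further and infer that the walk-distance comparison is biased by a calculable amount, or that baseline-adjusted ANCOVA would remove the bias. The documents support neither. Eligibility is settled before the baseline walk, and pre-screening uses an earlier one, so selection may act mainly on that earlier walk or on general fitness. The criterion for Class I and IV does not say which walk it means. Suppose selection on an earlier walk produces a baseline difference D between arms, there is no treatment effect, walks have equal variance, and baseline and follow-up correlate at r:

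- If all three walks are equally correlated, the follow-up difference is also D. The change comparison is unbiased (D − D = 0), and ANCOVA is biased by D − rD = (1 − r)D.
- If correlation decays with time (r, then r squared), the follow-up difference is rD. The change comparison is biased by rD − D = −(1 − r)D, and ANCOVA is unbiased.

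The two structures give opposite answers, and the plan does not say which applies. D is also unknown. A bias in metres, a false-positive rate or an ANCOVA remedy would rest on assumptions that cannot be checked here. Nor do the documents show that anyone has steered an allocation.

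**Conclusion.** The concern holds as a weakness in concealment, not as a demonstrated bias. The ceiling is firm: at most half of allocations (30 of 60) certain and a 75% best-guess rate, given sequential filling of pairs and knowledge of the first arm. The true figure lies between zero and that ceiling, depending on the order in which pair-mates were screened, tested and assigned. For second-of-pair subjects, the stated blinding of personnel through baseline and randomization is not assured. The size and direction of any resulting bias cannot be derived from the documents. The change is worth making because it is cheap and specific.

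**What to change.** 1. **Remaining subjects.** The existing independent randomizer replaces the pair rule with permuted blocks of randomly varying size, for example 4 and 6. The sizes are withheld from study staff and kept out of the protocol. The text states explicitly that each assignment is released only after that subject's eligibility decision and baseline tests are complete.
2. **Subjects already randomized.** From existing dates, report how many second-of-pair subjects were screened or baseline-tested after their pair-mate was allocated. This replaces the ceiling with a count. If the count is zero, the concern is answered for those subjects.

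The cost is a short amendment, a new list, a tabulation of dates and the larger temporary imbalance shown above. The protocol's aims of near-equal groups and no early filling are still met, with no extra patients or staff. The gain applies only to subjects not yet randomized, whose number the documents do not give, and it lies mainly in removing certainty.
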